To test the primary hypothesis H1a for our primary outcomes, we will use generalized linear mixed models to assess the effects of the intervention on each of the 6 SPPADE scores⁹⁰. All models will account for correlation of outcomes within clusters and across patients, and for changes in this correlation over time. We will adjust for time, measured by study period, to account for temporal effects. Each score will be adjusted for the prior score, with a coefficient that depends on the time t since the prior score; to account for potential changes in correlation of outcomes by over time we will include autoregressive terms at the patient level.⁹¹ To account for changing correlation within clusters over time we will incorporate a discrete-time correlation structure.⁹⁸

Our primary analysis will treat each SPPADE score as a continuous variable and employ a mixed effects generalized multivariate model; we will model all 6 scores jointly, which will allow us to account for the correlation between them and avoid correcting for multiple hypothesis tests.

Specifically, let Y_{ijkm} be the i^{th} score ($i=1,\dots,6$) of the j^{th} encounter for the k^{th} patient in the m^{th} cluster ($m=1,\dots,15$), for $j = 2,\dots$; the first score for each patient ($j=1$) is a baseline score collected during the first visit, not an outcome. Let $w=1,\dots,6$ indicate the trial step during which the survey is collected.

Then to test the hypothesis that the intervention impacts the 6 symptom scores we will estimate the joint models:

$$Y_{ijkm} = A_{ikm} + \mathbf{B}_i X_{jkm} + \mathbf{L}_i(t) Y_{i[j-1]km} + \mathbf{F} \mathbf{Z}_k + \mathbf{D} \mathbf{S}_m + \mathbf{Q} q_{jmk} + \mu_{imw} + \nu_{it} \quad ; \quad i=1,\dots,6 \quad (1)$$

where

X_{jkm} is an intervention indicator which equals 1 if encounter j for patient k in cluster m was post intervention and 0 otherwise;

\mathbf{B}_i is a vector of fixed effects for the intervention on symptom score i , $i = 1,\dots,6$;

\mathbf{L}_i is a vector of time dependent lags, representing the effect of the most recent measurement on the current one, as a function of time t in days between measures;

\mathbf{Z}_k is a vector of patient factors for patient k , \mathbf{F} is a corresponding vector of fixed effects;

\mathbf{S}_m is a cluster level set of indicators for randomization strata, \mathbf{D} is a vector of fixed effects;

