In the event that the model with patient surveys as the unit of analysis cannot be computed, we will use an alternative cluster-period model for the primary analysis. We will aggregate outcomes and covariates for each cluster for each time period and use these cluster-level estimates to assess the effect of the intervention. We will calculate the mean of each of the 6 different SPPADE NRS scores collected during trial cluster-periods. We will also calculate the mean baseline score for each participant that reports one or more ePROMs. We will then test the first primary hypothesis using a multivariate regression model using these 15 clusters \times 6 period = 90 cluster-period values, including an indicator for intervention status for each cluster-period, and adjusting for mean baseline scores and including indicators for study step to account for secular trends and for indicators for cluster to account for cancer type. We will adjust for cluster-period averaged values of factors of patients reporting during each period for which the SMD between intervention and control cluster-periods are >0.2 .

To assess the robustness of using the CP model, we will replicate the main analyses for each symptom NRS score. We will use the originally specified generalized mixed effects model, as well as the CP model adapted to the univariate dependent variable. This former model will be estimated at the survey level, with random effects for surveys within patients and patients within clusters; these 6 models (one for each symptom score) also included all pre-specified patient covariates, baseline symptom score, the lag in weeks since the baseline measurement and the interaction of the lag time with the baseline effect.

Because there is potential for the intervention to impact the baseline scores as well, we will replicate the cluster-period and survey level models each symptom score, including patients with only 1 survey score.

We will estimate models using the STAN software package.

Hypotheses H1b

To test whether the intervention has a differential effect on those patients with at least one elevated symptom score,

we will construct an indicator, E_{ijkm} , varying by measurement time, which indicates whether the i^{th} prior symptom score was elevated (>3). By interacting these indicators with the main intervention effects B_i we can assess the impact of the intervention on the corresponding scores of patients with at least one elevated score:

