$$Y_{ijkm} = A_{ikm} + B_i X_{jkm} + C E_{ijkm} + D_i E_{ijkm} X_{jkm} + L_i(t) Y_{i[j-1]km} + F Z_k + D S_m + Q q_{jmk} + \mu_{imw} + \nu_{it} \quad ; \quad i=1, \dots, 6 \quad (2)$$

We will then test the hypothesis as above by calculating the $PP[\text{Abs}(D_i) > 0, i=1, \dots, 6]$

In the event that the model with patient surveys as the unit of analysis cannot be computed to test Hypotheses H1b, we will use the cluster-period approach outlined for testing H1a, but will summarize SPPADE NRS scores for each cluster-period according to whether the patient had any prior elevated scores; we will then estimate a model analogous to the cluster-period model used to test Hypothesis H1a but including an indicator for post-elevation and the interaction with the intervention indicator.

Finally, as a secondary objective of this aim, to better understand the effectiveness of different components of the E2C2 intervention in reducing symptoms, we will perform a separate set of analyses to assess the impact of specific process measures (D.2.d) on SPPADE scores and other clinical outcomes. For each process measure we will first examine the distribution of values (frequency or duration) and, if highly skewed, categorize into 2 or more categories. We will then estimate for each outcome a mixed effects linear model with a random cluster effect, where the outcome is the dependent variable and the main independent variable is the continuous or categorized process measure, adjusting for patient covariates as described above. By testing for an overall process measure effect, we can assess which processes contribute most to reducing outcomes; we will also report measures of variance explained to enable relative comparison of process measure effects.

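### As printed, the H1b model has one shared elevated-score coefficient C for all six symptoms, so the interactions D_i that test H1b can differ from zero with no intervention effect

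*Combined protocol and SAP*

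**What the plan says.** H1b is one of two primary hypotheses. Under Hypotheses H1b, the plan defines an indicator E_ijkm that varies over time and equals 1 when the patient's i-th "prior symptom score was elevated (>3)". It then states: "By interacting these indicators with the main intervention effects B_i we can assess the impact of the intervention" on the corresponding scores. Model (2), written for i = 1 to 6, extends model (1) with "C E_{ijkm} + D_i E_{ijkm} X_{jkm}". The decision follows the H1a rule: "We will then test the hypothesis as above by calculating the" posterior probability for D_i.

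For the H1a model the plan says "we will model all 6 scores jointly". Its definitions there include:
- B_i, indexed by symptom.
- L_i, indexed by symptom, which "is a vector of time dependent lags, representing the effect of the most recent measurement on the current one".
- F, without a symptom index, which "is a corresponding vector of fixed effects". D (randomization strata) and Q (calendar time) are likewise unindexed and described as vectors.

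C appears only in model (2) and has no definition. The letter D does double duty there, as the strata coefficient and as the interaction D_i. All priors except those for calendar time are flat.

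**The concern.** In usual-care surveys (X = 0), model (2) as printed gives every symptom the same jump C when the prior score is above 3. In E2C2 surveys (X = 1) the jump is C + D_i, which is free for each symptom. If symptom i's own jump C_i differs from the pooled C, the model cannot show that in usual care but can in the intervention surveys. D_i therefore moves toward C_i minus C even when the intervention does nothing.

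The lag term need not remove this. E is a threshold of the same prior score that enters through L_i(t), so C_i measures departure from the fitted lag relation. That departure depends on each symptom's floor, skew and persistence. The plan itself expects many participants to report only mild symptoms or none, so a pile-up near the floor is plausible.

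The symptom-level H1b estimates and their credible intervals are at stake. Symptoms with a below-average jump would look as if E2C2 helped elevated patients, and those with an above-average jump as if it harmed them. This is misspecification, so more surveys only narrow the interval around the wrong value.

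**Working it through.** **The plan's own figure.** The Power Statement gives 70% power at a difference of 0.10 and nearly 100% at 0.20 (level 0.05). Its simulation inputs are not printed, so only consistency can be checked.
- Implied SE = 0.10/(1.960 + 0.524) = 0.0403.
- Power at 0.20 = Φ(0.20/0.0403 − 1.960) = 0.9987, which agrees.

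This power is for ν_1B, the main intervention effect. The documents give no figure for D_i.

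**Algebra, without a lag term.** Let the true jump be C_i in both conditions and the true D_i be 0. With intercepts and B_i specific to each symptom, the intervention surveys fit C + D_i = C_i exactly. C is then set by usual-care surveys, near the average jump C̄, so D_i = C_i − C̄. A symptom-specific lag slope absorbs part of this, leaving D_i ≈ λ(C_i − C̄) with λ below 1.

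**Simulation 1: jumps imposed.** From the documents: 15 clusters, 5 sequences, 6 periods, 6 symptoms. Assumed: variances, lag slopes, surveys per patient, and jumps spread evenly around a mean of 0.6. All B_i and D_i were zero. The fit was least squares with patient-by-symptom random-intercept weighting, L_i, symptom-specific period effects and patient-clustered SEs. The last row uses rounded, bounded 0-10 scores with no built-in jump, where symptoms differ only in mean and persistence.

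| True C_i | Replicates | Mean D_i, shared C | Mean D_i, C_i fitted |
|---|---|---|---|
| all equal | 4 | −0.02 to +0.02 | −0.03 to +0.02 |
| ±0.10 | 4 | −0.05 to +0.08 | −0.02 to +0.03 |
| ±0.25 | 18 | −0.15 to +0.16 | −0.02 to +0.03 |
| ±0.5 | 18 | −0.28 to +0.33 | −0.01 to +0.01 |
| ±1.0 | 4 | −0.57 to +0.69 | −0.02 to +0.02 |
| bounded, no built-in jump | 8 | −0.06 to +0.14 | −0.02 to +0.04 |

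- **Share passed into D_i (λ).** At ±0.25: 0.146/0.25 = 58% and 0.159/0.25 = 64%. At ±0.5: 0.275/0.5 = 55% and 0.330/0.5 = 66%. At ±1.0: 57% and 69%.
- **False signals at ±0.25.** The two extreme symptoms were rejected (two-sided 5%) in 94% and 100% of data sets. At least one of six was rejected in 18/18, against 6/18 with C_i; six independent 5% tests would give 1 − 0.95^6 = 26%. P(D_i < 0) reached 0.80 in 18/18 for the two lowest symptoms.
- **Sample size at ±0.25.** With about 119,000 symptom rows (SE 0.047) the extremes were −0.146 and +0.159. With about 191,000 rows (SE 0.037, 4 replicates) they were −0.139 and +0.164. The bias did not shrink.

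**Simulation 2: score shapes assumed.** 6,000 patients, 2-8 visits, scores 0-10, no intervention effect and a fitted patient intercept.
- Right-skewed patient means: D_i from −0.15 to +0.42 with shared C, against −0.05 to +0.06 with C_i.
- Mixture of never-symptomatic and chronic patients: −0.20 to +0.55, against −0.01 to +0.03.
- Gaussian latent scores: bias within 0.05.

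**Simulation 3: skewed, bounded 0-10 scores, 12 replicates.** D_i from about −0.12 to +0.35 with shared C, and within 0.02 with C_i. Gaussian scores showed no material bias under either.

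**The case against.** The strongest reply is that C was never meant to be shared. The plan describes a multivariate model with one equation per symptom, where each outcome would ordinarily have its own coefficients. F, D and Q also lack the symptom index, and the notation is loose elsewhere: D is used twice, and a random-effect vector for six scores is listed with five elements. This stands as a plausible reading. But F, D and Q are at least described as vectors, whereas C is not described at all. A programmer coding model (2) as printed would obtain one shared C.

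Second, the larger biases come from assumed shapes, and the plan provides for transforming scores toward normality where appropriate. None of the simulations tested that step, and the Gaussian case was benign. This limits any claim about size. It does not remove the problem, because a monotone transformation cannot separate a mass of tied scores at the floor, nor does it make the C_i equal.

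Third, the simulations simplify model (2). They use a least-squares analogue of the Bayesian fit, and few replicates where a count is given. They show direction and order of size, not this trial's bias.

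Fourth, the effect on the decision is limited. Read literally, the posterior probability that |D_i| exceeds 0 is 1 for any continuous posterior, with C or with C_i; that is a separate defect. Under a signed rule requiring all six symptoms, biases of both signs would not by themselves produce a benefit. The exposure is in symptom-level estimates, intervals and any signed rule applied symptom by symptom.

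**Conclusion.** The point holds for model (2) as printed and conditionally. If one C is fitted and the usual-care jumps differ between symptoms beyond the lag term, D_i absorbs part of the difference and can be non-zero when E2C2 has no effect. Under the assumed skewed or bounded shapes the largest biases were about 0.1 to 0.5 points, in either direction. With Gaussian scores or equal C_i they were negligible. The true spread of C_i is not in the documents.

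Four stronger readings are tempting and are not supported:
- **That H1b will be biased, or E2C2 falsely declared effective.** The subscript may simply have been dropped, the spread of C_i is unknown, and the printed rule does not respond to this bias.
- **That the bias exceeds the effect the plan is powered to detect.** The 0.10 figure belongs to the H1a main effect. No benchmark exists for D_i.
- **That rarely elevated symptoms such as depression are most exposed.** The documents give no elevation rates by symptom, so this would be an assumption.
- **That the cluster-period fallback has the same fault.** It is described as a multivariate regression, with no equation and no shared coefficient printed. It needs confirmation, not correction.

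**What to change.** In model (2), print the main effect as C_i and define it as one elevated-score coefficient per symptom. In the H1b cluster-period fallback, state that the post-elevation indicator also has a symptom-specific coefficient. Rename the strata coefficient so that D_i denotes only the interaction. If C_i was always intended, this is a clerical edit. If not, it adds five fixed effects (six in place of one), which is negligible in a survey-level model. No new data are needed.

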E2C2 / 18-007779

Enhanced, EHR-facilitated Cancer Symptom Control (E2C2)
Pragmatic Clinical Trial

NCT03892967

Document Date: 03/04/2025

IRB Minimal Risk Protocol Template

General Study Information

Principal Investigator: [name], MSCE

Study Title: Enhanced, EHR-facilitated Cancer Symptom Control (E2C2) trial

Protocol version number: March 4, 2025 Version 24

Research Question and Aims

Hypothesis: Collaborative care management for control of moderate or worse sleep disturbance, pain, physical function impairment, anxiety, depression, fatigue (SPPADE symptoms), and physical dysfunction among cancer survivors and patients with cancer will improve quality of life, symptom severity, and adherence to cancer treatment, and will also reduce need for acute care.

Aims:

Specific Aim 1. Conduct a cluster randomized pragmatic trial with a stepped wedge design to test the hypothesis that a symptom control-focused E2C2 intervention will significantly reduce SPPADE symptom and physical dysfunction scores; reduce unplanned hospitalizations, emergency department (ED) visits, and intensive care unit (ICU) admissions; improve adherence to cancer therapies; and improve self-reported quality of life.

H1a. SPPADE symptom scores will improve more, relative to prior scores, for patients who have been exposed to the intervention when compared with the improvement of patients that are not exposed.

H1b. Among patients who report moderate or worse symptoms, SPPADE symptom scores will improve more for patients who have been exposed to the intervention when compared with the improvement of patients that are not exposed.

Specific Aim 2. Evaluate the hypothesis that use of a multifaceted, evidence-based implementation strategy to support adoption and use of the E2C2 system will result in improvements in implementation and clinical outcomes.

Specific Aim 3. Conduct a mixed methods evaluation to detect, understand and reduce disparities in the adoption and implementation of the E2C2 intervention among elderly and rural-dwelling patients with cancer.

Background:

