We will summarize patient-, cluster-, and survey-level characteristics (e.g., sex, age, cancer type and stage, insurance status) by intervention status (pre-E2C2, E2C2) of the encounter. All analyses will be conducted on an intention to treat basis. The primary analysis will test differences in change in joint SPPADE symptom NRS scores in all participants, and in those who report elevated (4-10/10) symptoms, between participants who are exposed to the intervention and those who are not. We have two primary hypotheses. The first will assess the effect of the intervention across the full cohort of patients enrolled, Hypothesis *H1a*. The second will assess the effect of the intervention among patients who report moderate or worse symptoms, Hypothesis *H1b*. The rationale for Hypothesis *H1b* is that some intervention components are only offered to participants who report elevated symptom scores. Additionally, a large proportion of the trial cohort will only report mild or no symptoms. Among these participants there is little or no opportunity to improve symptoms and no practical exposure to the intervention. The original hypotheses regarding population-level effects will retain primary importance, yet it is critical to test intervention effects in the subset of patients that ever have elevated symptom scores.

We will include a common set of variables in all models testing the effectiveness of the intervention. Cancer type and stage will be included, as well as 7 variables selected as likely to impact the use of the portal and completion of the

[figure not shown]

Figure 3. Power simulations for E2C2 Interventions

surveys: from the EHR we will capture age (categorized into 10-year increments), sex (male or female), and severity of illness (Elixhauser score as a categorical variable). We will also link the patient 9-digit zip code to Census data to get estimates of educational level, income, and broadband access, which will be categorized into quartiles.

Hypotheses H1a

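### H1b's symptomatic group is defined one way in model (2) and another in the cluster-period fallback, so the two analyses of one primary hypothesis estimate different effects

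*Combined protocol and SAP*

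**What the plan says.** All places are in the combined protocol and SAP.

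- Aims, H1b: "Among patients who report moderate or worse symptoms, SPPADE symptom scores will improve more" with exposure to the intervention than without. This is worded at patient level.
- Data Analysis Plan, Specific Aim 1, rationale: H1b is needed because some components go only to patients reporting elevated scores, and many patients will report only mild or no symptoms. "Among these participants there is little or no opportunity to improve symptoms and no practical exposure to the intervention". The paragraph ends: "it is critical to test intervention effects in the subset of patients that ever have elevated symptom scores".
- Hypotheses H1b, lead-in to model (2): the test is whether the intervention "has a differential effect on those patients with at least one elevated symptom score".
- Hypotheses H1b, model (2): the indicator E carries a symptom index and is described as "varying by measurement time, which indicates whether the i^{th} prior symptom score was elevated (>3"). Its interaction with the intervention, D_i, is what is tested.
- Hypotheses H1b, fallback if the survey-level model cannot be computed: the analysis "will summarize SPPADE NRS scores for each cluster-period according to whether the patient had any prior elevated scores" and fits a model "including an indicator for post-elevation and the interaction with the intervention indicator".

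**The concern.** The two H1b analyses sort the same scores differently. Take a patient with a single anxiety score of 5 early on and pain of 0 ever since. Model (2) puts every later pain score in the non-elevated group. The fallback, read plainly, puts every later pain score in the elevated group, because the patient has a prior elevated score and nothing switches the flag off.

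The fallback is a pre-specified route to the primary result, used when computation fails. A failure to fit would change the estimation method and also the population and effect being reported, under the same hypothesis label. A benefit concentrated in currently elevated symptoms could appear under one route and be much reduced under the other.

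**Working it through.** **1. The plan's own figure.** The Power Statement gives 70% power at a difference of 0.10 and nearly 100% at 0.20 (5% level). It is not an H1b figure, and its variance inputs are not printed, so it cannot be reproduced. It is internally consistent: SE = 0.10 / (1.960 + 0.524) = 0.04025, and 0.20 / 0.04025 − 1.960 = 3.01, or 99.9% power. It gives no benchmark for H1b.

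**2. The definitions side by side.**

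| Place | Which symptom | Which time |
|---|---|---|
| Model (2) indicator | same symptom i | prior score, varying by measurement |
| Fallback | none specified | any prior, post-elevation |
| Rationale | none specified | ever |
| Lead-in to model (2) | at least one elevated score | not stated |

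The cut-point is not in dispute: 4-10 and >3 coincide on an integer scale.

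**3. Attenuation, conditional on one premise.** Let E_i = 1 if symptom i was elevated at the prior survey, and G = 1 if any symptom was elevated at any prior survey. Suppose the extra effect D exists only when E_i = 1. Ignoring time trends, the fallback interaction estimates

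D × [P(E_i=1 | G=1) − P(E_i=1 | G=0)].

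E_i = 1 forces G = 1, so the second term is 0 and the first is p / P(G), where p is the per-symptom prevalence of an elevated score. With model (2)'s grouping the factor is 1 by definition.

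**4. Size.** The documents give no prevalence or persistence, so these inputs are assumed: p from 10% to 50%; (between-symptom, between-visit) correlations of (0.4, 0.5), (0.5, 0.7) or (0.7, 0.8); 1, 3 or 6 prior surveys. P(G) comes from a latent-Gaussian simulation of six symptoms. Selected rows of the 45 scenarios:

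| p | Correlations | Prior surveys | P(G) | p / P(G) | Some symptom elevated at last survey, given G |
|---|---|---|---|---|---|
| 0.10 | 0.4, 0.5 | 6 | 0.76 | 0.13 | 0.46 |
| 0.20 | 0.5, 0.7 | 3 | 0.73 | 0.27 | 0.72 |
| 0.30 | 0.5, 0.7 | 3 | 0.85 | 0.35 | 0.79 |
| 0.40 | 0.7, 0.8 | 3 | 0.82 | 0.49 | 0.83 |
| 0.50 | 0.7, 0.8 | 1 | 0.78 | 0.64 | 1.00 |

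The factor runs from 0.13 to 0.64 overall, and from 0.22 to 0.49 at 20-40% prevalence with 3 or 6 prior surveys. It is below 0.50 in 33 of the 36 scenarios with prevalence up to 40%. If the fallback's phrase is read as same symptom but ever, the factor is 0.31 to 0.76 with 3 or 6 prior surveys and 1.00 with one.

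**5. Calendar time.** A flag that never switches off gathers patients as follow-up lengthens, so the composition of both groups drifts. In a stepped wedge, exposure also rises with calendar time. The fallback names step indicators common to both groups, so a difference in drift between groups can load onto the interaction.

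Two illustrative simulations of the cluster-period regression (15 clusters, 6 periods) used assumed inputs and a 0.5-point benefit only when the symptom was elevated:

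- With open enrolment and 12 runs, model (2)'s grouping recovered 0.44 and the any-prior grouping 0.11, a ratio of 0.11 / 0.44 = 0.25. The flagged share rose from about 66% to 85% of scores across steps.
- A second check recovered about 0.50 and essentially none. There the any-prior grouping shifted the interaction by about 0.07 to 0.24 with no true effect.

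The shift depends on patient turnover: it is larger when the same patients are followed throughout and can be negligible when patients enter and leave steadily.

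**The case against.** The strongest reply is that the fallback is not the departure. H1b is worded at patient level, the rationale says ever elevated, and the lead-in says at least one elevated score. All three are nearer the fallback than model (2)'s indicator. This stands, and the point is therefore an inconsistency, not an error located in the fallback.

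A reader might go on to infer three stronger things that the documents do not support.

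- *The fallback group is mostly non-symptomatic.* No document figure shows this. In the assumed scenarios 46-100% of the flagged group had at least one symptom elevated at the last survey, with less than half in only one of 45. What is plausible is that most flagged scores are not elevated on the symptom being analysed.
- *The fallback readmits the patients whom the rationale sets aside.* Those are patients who only ever report mild or no symptoms, and the fallback keeps them out of its elevated group.
- *Dilution is certain.* It requires the benefit to be confined to the symptom elevated at the prior survey. The Background section argues against treating symptoms in isolation, and spillover or lasting benefit would reduce the loss.

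Two further limits apply. The plan provides for computational failure without predicting it, and describes Markov Chain Monte Carlo as very effective for such models. The robustness replication it specifies sits under H1a, so no planned H1b comparison is lost.

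**Conclusion.** The inconsistency is established from the text alone. Model (2) and its fallback use different groups for one primary hypothesis, and the surrounding text does not settle which is meant. Switching to the fallback changes the quantity estimated.

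The numerical consequence is conditional. The factor of 0.13 to 0.64 rests on assumed prevalence, correlations and survey counts, and on benefit being confined to symptoms elevated at the prior survey. The calendar-time bias is a real mechanism, but its size depends on patient turnover, which the documents do not give. The plan should be corrected before analysis. Nothing here shows that H1b cannot be tested.

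**What to change.** State one H1b definition, covering both choices (same symptom or any; most recent or ever), and use it in the hypothesis text, model (2) and the fallback.

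- **Default:** keep model (2)'s indicator. In the fallback, split each symptom's cluster-period scores by whether the patient's preceding appointment-linked score for that symptom was >3, and form separate E=1 and E=0 means. Reword the rationale and lead-in to match. Report the any-prior-elevated version as a labelled sensitivity analysis.
- **If ever elevated is the intended target:** change model (2)'s indicator to match, say whether it covers one symptom or any, and let step effects differ by post-elevation group in the fallback. With 6 steps this adds 5 coefficients per symptom.

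The cost is SAP wording and a regrouping of data already held. The default gives noisier E=1 means in small cluster-periods. It also moves a patient whose score falls below 4 into E=0, so benefit sustained after that point is counted there; a post-elevation flag would keep that patient. The sponsor should record which trade-off it accepts.
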